## Appendix E(a) : Mother's Questionnaire

### (English version) QUESTIONNAIRE I : MOTHER

Dear Madam,

Thank you for agreeing to participate in the research.

The purpose of this research is to evaluate the effectiveness of Kangaroo Care (KC) among mother with premature infant in NICU.

The questionnaire consists of:

Section A : Demographic Characteristic

Section B : Part I - Perception on KC  
Part II - Knowledge on KC  
Part III - Barrier on KC  
Part IV - Parenteral Stress Scale: Neonatal Intensive Care Unit

Please answer **ALL** the questions to the best of your ability and as honestly as possible.  
Thank you for your cooperation and support in this research.

## SECTION A : Demographic Characteristic

**Instruction:** Please ✓ to your response.

**1. Age** \_\_\_\_\_ (*Please fill in the blank*)

**2. Race**

01. Malay  02. Chinese  03. Indian  04. Others \_\_\_\_\_ (*please specify*)

**3. Religion**

01. Islam  02. Buddha  03. Hindu   
04. Others \_\_\_\_\_ (*please specify*)

**4. Marital Status**

01. Married  02. Single  03. Divorced  04. Widowed  05. Engaged

**5. Delivery type**

01. SVD  02. Caesarean section (CS)

**6. Parity of mother**

01. Primipara  02. Multipara

**7. Highest Educational Level**

01. Primary  02. Secondary  03. Tertiary

**8. Occupation status**

01. Working  02. Not working

**9. Employment sector status**

01. Government  02. Private

**10. Maternity leave status**

01. 60 consecutive days  02. 30 consecutive days

**11. Household income (RM)**

01. 500 – 999  02. 1000 – 1499  03. 1500 – 1999  04. 2000 – 2499   
05. 2500 – 2999  06. ≥ 3000  07. ≥ 4000

**2. Breast feeding status**

Do you breast fed or express breast milk (EBM) for your baby?

01. Yes  02. No

**13. Post-partum stress status (pre-post)**

01. Yes  02. No

14. Kangaroo care knowledge

01. Yes  02. No  If Yes;.....If No:.....

Before you bexperimental groupin completing the survey, please answer the following question, then go on to the Section B

Do you practice KC in NICU? (Circle your response)

1 - NO

2 - YES

## SECTION B: Kangaroo Care (KC) Survey

**Instruction:** Please answer the following questions. Use the following scale for your responses.

5 = Strongly Agree

4 = Agree

3 = Neither Agree Nor Disagree

2 = Disagree

1 = Strongly Disagree

### Part I: Mother's Perception of KC

No	Statement	5	4	3	2	1
1	All preterm babies should be allowed to participate in KC regardless of age.					
2	All preterm babies should be allowed to participate in KC regardless of weight.					
3	Babies receiving IV fluids should NOT be allowed to participate in KC.					
4	KC encourages the parenting role.					
5	KC enhances the attachment process between mother and baby.					
6	KC interrupts babies care giving.					
7	KC should be available only to breastfeeding mothers.					
8	KC is NOT feasible with some babies.					
9	KC keeps mothers too tied to the bedside.					
10	KC should be offered to all mothers in the NICU.					
11	KC will benefit preterm babies.					
12	KC will help mothers feel more confident in caring for their preterm babies.					
13	KC will improve the baby's outcome.					
14	KC will interfere with the completion of my tasks.					
15	Learning about KC will help me be a better mother.					
16	Nurses look forward to introducing KC to a new mother.					
17	My babies have adequate time for mother-baby contact without the use of KC.					
18	The increased amount of time required to prepare a baby for a KC session is out of proportion to the benefits.					
19	The teamwork required between nurses and mothers when doing KC is worth the effort.					
20	There is NOT enough flexibility in the NICU to allow mothers extended visits (more than 1 hour) for KC.					

## Part II: Knowledge on KC

**Instruction:** Please answer the following questions to the best of your ability based on your own personal knowledge of KC, **NOT** on its practice. Circle your response that best represents to knowledge of KC. Use the following scale for your responses:

3 = True

2 = False

1 = Don't know

No	Statement	True	False	Not sure
1	Babies appear to be satisfied in KC.	3	2	1
2	Babies on phototherapy can participate in KC.	3	2	1
3	Babies typically decrease heart rate during KC.	3	2	1
4	Babies with peripheral IVs can participate in KC.	3	2	1
5	KC has been shown to improve breathing patterns in preterm babies.	3	2	1
6	KC is contraindicated in premature babies.	3	2	1
7	KC is contraindicated in babies weighing less than 1000 grams.	3	2	1
8	KC is now considered safe as an alternative approach to care for preterm babies.	3	2	1
9	Most babies experience a decrease in temperature during KC.	3	2	1
10	KC increase risk of infection in premature babies.	3	2	1
11	KC cause more stress with heart problem babies.	3	2	1

## Part III: Perceived Barriers on KC

**Instruction:** Please indicate a very important perceived barrier of KC. Use the following scale for your responses:

5 = Very Influential

4 = Somewhat Influential

3 = Neither Influential Nor Non-Influential

2 = Not Very Influential

1 = Not Influential at All

No	Statement	5	4	3	2	1
1	Mothers' reluctance to allow KC.					
2	Mothers' belief that technology (e.g., incubators) is more beneficial to premature babies than care a mother can provide.					
3	Mothers' felt no privacy during KC.					
4	Mothers' difficult to assess baby's readiness for KC.					
5	Mothers' reluctance to initiate KC.					
6	Mothers' reluctance to participate in KC.					
7	Mothers' is frequently unavailable to do KC.					
8	Mothers' fear of safety for babies below a certain weight.					
9	Mothers' fear of low temperature during KC.					
10	Mothers' fear of baby's does not breastfeed during KC.					
11	Mothers' feel inability to provide adequate time to other children during KC.					
12	Mothers' belief that KMC is used for babies who are NOT developmentally well.					
13	Mothers' discomfort with exposing their chest during KC.					
14	Mothers' belief that will be much disturbance to the baby during KC.					
15	Mothers' unable to come to visit the baby for a long period of time.					
16	Mothers' felt nursing staff reluctance to participate in KC.					
17	Mothers' feel that KC adds a burden to nurses, inadequate time due to working commitment.					
18	Mothers' felt that KC makes it difficult to nurses to administer care.					
19	Mothers' felt the nursing staff's lack of exposure for mothers participating in KC.					

#### Part IV: PARENTAL STRESS SCALE: NEONATAL INTENSIVE CARE UNIT

**Instruction:** On the questionnaire, circle the single number that best expresses how stressful each experience has been for you. The numbers indicate the following levels of stress:

5 = Extremely stressful

4 = Very stressful

3 = Moderately stressful

2 = A little stressful

1 = Not at all stressful the experience did not cause you to feel upset, tense, or anxious

No	Items	5	4	3	2	1
1.	Being separated from my baby	5	4	3	2	1
2.	Not feeding my baby myself	5	4	3	2	1
3.	Not being able to care for my baby myself (for example, diapering, bathing)	5	4	3	2	1
4.	Not being able to hold my baby when I want	5	4	3	2	1
5.	Feeling helpless and unable to protect my baby from pain and painful procedures	5	4	3	2	1
6.	Feeling helpless about how to help my baby during this time	5	4	3	2	1
7.	Not having time alone with my baby	5	4	3	2	1

\_\_\_\_\_ Thank you for your participating in this study \_\_\_\_\_

## Appendix E (b): Questionnaire Mother (Malay Version)

University of Malaya

### SOAL SELIDIK II: IBU

Puan yang dihormati,

Terima kasih kerana bersetuju untuk mengambil bahagian di dalam kajian ini.

Tujuan kajian ini adalah untuk menilai keberkesanan Kangaroo Care (KC) di kalangan ibu dengan bayi pra-matang di NICU.

Soal selidik ini terdiri daripada:

Bahagian A : Ciri-ciri demografi

Bahagian B : Bahagian I - Persepsi terhadap KC

Bahagian II - Pengetahuan terhadap KC

Bahagian III - Halangan terhadap KC

Bahagian IV - Skala Stres Parenteral : Unit Rawatan Rapi Neonatal

Sila jawab **SEMUA** soalan dengan jujur dan paling tepat. Terima kasih diatas kerjasama dan sokongan anda dalam kajian ini.

**Seksyen A : Ciri-ciri Demografik**

**Arahan** : Sila tandakan  pada respon anda.

1. **Umur** \_\_\_\_\_ (*sila isi tempat kosong*)

**2. Bangsa**

01. Melayu  02. Cina  03. India  04. Lain-lain \_\_\_\_\_ (*sila nyatakan*)

**3. Agama**

01. Islam  02. Buddha  03. Hindu  04. Lain-lain \_\_\_\_\_ (*sila nyatakan*)

**4. Status Perkahwinan**

01. Berkahwin  02. Belum berkahwin  03. Bercerai  04. Janda  05. Bertunang

**5. Kelahiran secara**

01. Normal  02. Pembedahan

**6. Status kelahiran ibu**

01. Kelahiran pertama kali  02. Kelahiran lebih dari satu kali

**7. Tahap Akademik**

01. Sekolah Rendah  02. Sekolah Menengah  03. Universiti

**8. Status pekerjaan**

01. Bekerja  02. Tidak bekerja

**9. Status sektor pekerjaan**

01. Kerajaan  02. Swasta

**10. Status cuti bersalin**

01. 60 hari berturut-turut  02. 30 hari berturut-turut  03. 90 hari berturut -turut

**11. Pendapatan isi rumah (RM)**

01. 500-999  02. 1000-1499  03. 1500-1999  04. 2000-2499

05. 2500-2999  06.  $\geq 3000$   07.  $\geq 4000$

**12. Status penyusuan susu badan.**

Adakah anda menyusu atau memerah susu (EBM) untuk bayi anda?

01. Ya  02. Tidak

**13. Status stres selepas bersalin (pre-pos)**

01. Ya  02. Tidak

Sebelum anda mula melengkapkan soal kaji selidik ini, sila jawab soalan berikut, kemudian pergi ke Seksyen B.

Pernahkah anda mengamalkan KC ? (Bulatkan jawapan anda)

1 - YA      2 - TIDAK

## SEKSYEN B : Kangaroo Care (KC) Survey

**Arahan :** Sila jawab soalan-soalan berikut. Gunakan skala berikut untuk jawapan anda.

5 = Sangat Setuju

4 = Setuju

3 = Berkecuali

2 = Tidak setuju

1 = Sangat Tidak Setuju

### Bahagian I : Persepsi terhadap KC

No	Statemen	5	4	3	2	1
1	Semua bayi pramatang harus dibenarkan untuk mengambil bahagian dalam KC tanpa mengira usia.					
2	Semua bayi pramatang harus dibenarkan untuk mengambil bahagian dalam KC tanpa mengira berat badan.					
3	Bayi yang menerima cecair Intra Vena TIDAK harus dibenarkan untuk mengambil bahagian dalam KC.					
4	KC menggalakkan peranan keibubapaan.					
5	KC meningkatkan proses sayang antara ibu dan bayi.					
6	KC mengganggu penjagaan bayi.					
7	KC hanya perlu diberi kepada ibu-ibu yang menyusukan anak sahaja.					
8	KC TIDAK dilaksanakan kepada sesetengah bayi.					
9	KC menyebabkan ibu perlu sentiasa terikat berada disisi bayi.					
10	KC perlu ditawarkan kepada semua ibu-ibu di NICU.					
11	KC akan memberi manfaat kepada bayi pramatang.					
12	KC akan membantu ibu berasa lebih yakin dalam menjaga bayi pramatang mereka.					
13	KC meningkatkan pertumbuhan yang baik kepada bayi.					
14	KC akan mengganggu saya menyelesaikan tugas-tugas saya.					
15	Belajar mengenai KC akan membantu saya menjadi ibu yang lebih baik.					
16	Diharap jururawat dapat memperkenalkan KC untuk ibu yang baru.					
17	Bayi saya mempunyai masa yang mencukupi untuk bersentuhan diantara ibu dan bayi tanpa menggunakan KC.					
18	Jumlah masa yang diperlukan untuk menyediakan bayi bagi sesi KC tidak setanding dengan faedah.					
19	Kerja berpasukan amat diperlukan diantara jururawat dan ibu apabila melakukan KC.					
20	Tidak ada fleksibiliti masa yang cukup dalam NICU untuk membenarkan para ibu dilanjutkan masa (lebih daripada 1 jam) untuk KC.					

## Bahagian II : Pengetahuan terhadap KC

**Arahan** : Sila jawab soalan-soalan berikut dengan tepat mengikut kemampuan anda berdasarkan pengetahuan peribadi anda sendiri mengenai KC, **TIDAK** pada amalannya. Bulatkan jawapan yang terbaik untuk mewakili pengetahuan KC anda. Gunakan skala berikut untuk jawapan anda:

3 = Benar

2 = Salah

1 = Tidak pasti

No	Statemen	Betul	Salah	Tidak Pasti
1	Bayi kelihatan berpuas hati dengan KC.	3	2	1
2	Bayi dengan rawatan fototerapi boleh mengambil bahagian dalam KC.	3	2	1
3	Bayi biasanya mengurangkan kadar jantung ketika KC.	3	2	1
4	Bayi dengan Intra periferal boleh mengambil bahagian dalam KC.	3	2	1
5	KC telah membuktikan dapat membantu kadar pernafasan pada bayi pramatang.	3	2	1
6	KC tidak sesuai pada bayi pramatang.	3	2	1
7	KC tidak sesuai pada bayi yang berat kurang daripada 1000 gram.	3	2	1
8	KC kini dianggap selamat sebagai pendekatan alternatif untuk menjaga bayi pramatang.	3	2	1
9	Kebanyakan bayi mengalami penurunan suhu semasa KC.	3	2	1
10	KC adalah peningkatan risiko jangkitan pada bayi pramatang.	3	2	1
11	KC tidak sesuai untuk bayi yang mempunyai masalah jantung.	3	2	1

### Bahagian III : Halangan terhadap KC

**Arahan :** Sila nyatakan halangan yang dilihat sangat penting dalam KC. Gunakan skala berikut untuk jawapan anda:

5 = Sangat Penting

4 = Agak Penting

3 = Tidak Penting Nor Tidak Penting

2 = Tidak Sangat Penting

1 = Tidak Penting Lansung

No	Statemen	5	4	3	2	1
1	Ibu enggan untuk melakukan KC.					
2	Ibu percaya bahawa teknologi (contohnya, inkubator) adalah lebih bermanfaat untuk bayi pra-matang daripada jagaan yang disediakan oleh seorang ibu.					
3	Ibu merasakan tiada privasi semasa melakukan KC.					
4	Ibu sukar untuk menilai kesediaan bayi untuk KC.					
5	Ibu enggan untuk memulakan KC.					
6	Ibu enggan untuk terlibat dalam KC.					
7	Ibu sering tidak tersedia untuk melakukan KC.					
8	Ibu takut akan keselamatan bayi pada berat badan yang tertentu untuk memulakan KC.					
9	Ibu takut bayi kesejukan semasa KC.					
10	Ibu takut bayi tidak menyusu semasa KC.					
11	Ibu merasa tidak mempunyai masa yang cukup untuk diberi kepada anak-anak lain semasa KC.					
12	Ibu percaya yang KC hanya diberi kepada bayi yang mempunyai masalah perkembangan.					
13	Ibu merasa tidak selesa bahagian dada mereka terdedah semasa KC.					
14	Ibu percaya bahawa akan banyak mengganggu bayi semasa KC.					
15	Ibu tidak dapat datang untuk melawat bayi untuk tempoh masa yang lama.					
16	Ibu merasa jururawat enggan membantu semasa mengambil bahagian dalam KC.					
17	Ibu percaya bahawa KC akan menambah kerja dan komitmen jururawat kerana kesuntukan masa.					
18	Ibu percaya KC akan menyukarkan tugas jururawat dalam memberi penjagaan dan rawatan kepada bayi.					
19	Ibu berasa jururawat kurang diberi pendedahan tentang KC untuk ibu-ibu yang mengambil bahagian di dalam KC.					

#### **Bahagian IV: SKALA PARENTAL STRES : UNIT JAGAAN INTENSIVE NEONATAL**

**Arahan** : Sila bulatkan nombor berikut untuk menyatakan bagaimana pengalaman tekanan anda ketika bayi berada di NICU. Nombor berikut menunjukkan tahap tekanan tersebut:

5 = Sangat tertekan

4 = Sangat tertekan

3 = Agak tertekan

2 = Sedikit tertekan

1 = Tidak sama sekali tertekan pengalaman tidak menyebabkan anda berasa kecewa, texperimental groupang, atau cemas

No	Item	5	4	3	2	1
1.	Dipisahkan daripada bayi saya.					
2.	Tidak memberi makan bayi saya sendiri					
3.	Tidak mampu untuk menjaga bayi saya sendiri (contohnya, menukar lampin dan mandi)					
4.	Tidak dapat memexperimental groupang bayi saya apabila saya mahu.					
5.	Rasa tidak berdaya dan tidak dapat melindungi bayi saya dari prosedur sakit dan menyakitkan.					
6.	Rasa tidak berdaya tentang bagaimana untuk membantu bayi saya pada masa ini.					
7.	Tidak mempunyai masa untuk bersama dengan bayi saya.					

\_\_\_\_\_ Terima kasih kerana menyertai dalam kajian ini \_\_\_\_\_

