The PSS scores reported in the NICU validation test ranged from 0.70 to 0.98. Miles' latest revision is a self-report scale of 26 items that measure parental stress related to three NICU situations: NICU sight and sound (5 items), baby appearance, behavior, and treatments (14 items), and alteration of relationship and parental roles (7 items). The researchers in this study have used the Parental Stressor Scale: Neonatal Intensive Care Unit (PSS: NICU: P&R). Confirmatory factor analysis (CFA) to confirm the appropriateness of this instrument for the current setting, statistical methods performed to test the reliability of this question is to evaluate through Cronbach's alpha in this section was carried out on this part of the questionnaire (PSS: NICU: P&R). All seven (7) items were positively and negatively worded as shown in (Appendix B). Out of seven items, there were five positive statements, which were (1,3,4,5,7), and two negative statements, which were (2 and 6). A 5-point response Likert scale was used: not stressful at all (1), a little stressful (2), moderately stressful (3), very stressful (4), and extremely stressful (5). In the current study, PSS:NICU:P&R scores were categorized based on Chourasia et al., 2013, who rated level of stress as high-level stress (4-5), moderate level stress (3-3.99) and low stress (1-2.99). Scoring was presented as a mean score. For the purpose of KC-EP and kangaroo care implementation, maternal level of stress was further categorized. A higher score showed a higher stress level with reference to the descriptors; a high level was (3-5) and a low level was (1-2.99). The stress scores were calculated and converted into mean scores, then categorized into two (2) groups. The highest mean scores of  $M=2.63$  and below indicated a low level of stress while mean scores above  $M= 2.63$  indicated a high level of stress related to preterm infant's admission to NICU.

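### The Malay stress scale prints one label for points 4 and 5, so the top of the scale is not verbally equivalent to the English form; the effect on the stress result is of unknown size and direction

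*Combined protocol and SAP*

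**What the plan says.** Section 3.8 (Research Instrument) provides Questionnaire I for mothers in English and in a Malay translation. Sections 3.16.1 and 3.16.2 offer both versions to both groups. Part IV measures stress with seven items on a five-point scale.

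- **Methods** (section 3.8.1, Part IV): the points are "not stressful at all (1), a little stressful (2), moderately stressful (3), very stressful (4), and extremely stressful (5").
- **English form** (Appendix E(a), Part IV): "5 = Extremely stressful" and "4 = Very stressful".
- **Malay form** (Appendix E(b), Bahagian IV): "5 = Sangat tertekan" and "4 = Sangat tertekan".

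The methods turn the item scores into a mean and divide mothers at 2.63. Stress belongs to specific objective 1 and hypothesis H1. Section 3.19.1 and Table 3.4 analyse it with repeated-measures GLM. Neither mentions form language as a covariate or stratum.

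A separate question stands just before Section B of each form. The English asks "Do you practice KC in NICU? (Circle your response") with 1 = No and 2 = Yes. The Malay asks "Pernahkah anda mengamalkan KC ? (Bulatkan jawapan anda") with 1 = Ya (yes) and 2 = Tidak (no). The Malay wording means ever having practised KC and does not mention the NICU.

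**The concern.** A mother using the Malay form meets two numbers with one verbal meaning at the top of the scale. A mother using the English form does not. Because the outcome is a mean of the raw points, the choice between 4 and 5 enters the score and can carry a mother across a category boundary.

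The groups were recruited one after the other without randomisation, so nothing in the design balances form language between them. Language is not among the fourteen maternal characteristics listed for Section A of Questionnaire I, so an imbalance would not be seen or adjusted for. The plan does not say in words that the two versions are pooled. That is inferred from the absence of any analysis by language.

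The KC-practice item raises a smaller, separate question: the same printed code means opposite things in the two forms, and the two questions cover different periods and settings.

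**Working it through.** The plan gives no figure on this point to reproduce. The check is a comparison of the forms followed by arithmetic on the seven-item mean.

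**1. Labels side by side**

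| Point | Methods and English form | Malay form |
|---|---|---|
| 5 | extremely stressful | Sangat tertekan |
| 4 | very stressful | Sangat tertekan |

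Only these two points share a label in the Malay form.

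**2. Effect on one mother's score.** One item marked 5 instead of 4 changes the mean by 1/7 = 0.14. If all seven move the same way, the change is 7/7 = 1.0. The methods call items 2 and 6 negative statements but do not say for this scale whether they are reverse-scored. If they are, a move from 4 to 5 on either lowers the mean by 0.14, and all seven moving together gives (5 − 2)/7 = 0.43.

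**3. Effect on categories, before any reverse scoring**

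- Three items at 4 and four at 1: (12 + 4)/7 = 2.29, below 2.63. With the three marked 5: (15 + 4)/7 = 2.71, above 2.63.
- Five items at 4 and two at 2: (20 + 4)/7 = 3.43, moderate in the three-band scheme that section 3.8.1 also cites. With the five marked 5: (25 + 4)/7 = 4.14, high.

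**4. Effect on the group comparison.** Let m be the share of mothers using the Malay form and s their average net shift. The spurious difference is m_E·s_E − m_C·s_C, for the experimental (E) and control (C) groups. It is zero if both m and s are equal in the two groups. With a common s it is (m_E − m_C)·s. The documents give neither m nor s, so these are assumptions:

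| Difference in Malay share | s = 1/7 | s = 0.5 |
|---|---|---|
| 10 points | 0.014 | 0.05 |
| 20 points | 0.029 | 0.10 |
| 30 points | 0.043 | 0.15 |

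The range is about 0.01 to 0.15 points.

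**5. KC-practice item, only if printed codes are pooled without recoding.** With true yes rate p, the apparent rate is (1 − m)p + m(1 − p), ignoring the difference in wording. For an assumed p = 20%:

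- m = 25%: 0.75 × 0.20 + 0.25 × 0.80 = 35%
- m = 50%: 0.50 × 0.20 + 0.50 × 0.80 = 50%
- m = 75%: 0.25 × 0.20 + 0.75 × 0.80 = 65%

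**The case against.** **The order of the scale survives.** The Malay instruction asks the mother to circle a number, and the numbers run from 5 to 1, so many mothers will still read 5 as more than 4. This stands and limits the effect. It does not restore a verbal distinction between the two points.

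**Opposite moves cancel.** A reader might infer a definite shift: if 20 to 40% of answers lie in the top two points and half of them land on the other label, a mother's mean moves by 0.2 × 0.5 × 1 = 0.1 to 0.4 × 0.5 × 1 = 0.2. That requires every displaced answer to move the same way. If intended 4s become 5 as often as intended 5s become 4, the net shift is zero. The documents support neither the shares nor a direction.

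**No imbalance between groups is shown.** Both groups come from the same unit under the same eligibility criteria, and both were offered both versions. This stands: a group bias is possible but not demonstrated.

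**Repeated measures absorb part of it.** If a mother keeps one language version throughout, which the plan does not state, a constant offset largely drops out of the group-by-time comparison. It does not drop out fully if use of the top points changes over time.

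**Translation and reliability work was done.** Sections 3.19.3 to 3.20.1 report forward and backward translation, expert review and a bilingual pilot of 30 mothers with alpha 0.951 for stress. None of this corrects the printed label, and alpha measures internal consistency, not equivalence of labels between languages.

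**The KC-practice item has no stated analytic role.** It is not among the fourteen listed maternal variables and does not appear in section 3.19.1 or Table 3.4. KC exposure is taken from hours in the progress booklet. This stands and makes the item secondary.

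**The copy may not be the administered form.** The Malay appendix contains find-and-replace damage inside words. That did not create the duplicate label, but it is a reason to check the form actually used.

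**Conclusion.** The defect holds as printed: points 4 and 5 of the Malay stress scale share a label, against five distinct labels in the English form and the methods, in an outcome scored as a mean and split at 2.63.

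Its size and direction cannot be determined from the documents. Per item the stake is 0.14 on the mean. The group effect of about 0.01 to 0.15 rests on an assumed 10 to 30 point difference in Malay share, a common net shift of 0.14 to 0.5, and pooling of the versions, which is inferred.

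Two stronger readings are not supported. One is that English and Malay answers as a whole are on different scales, or that the stress result is biased: the label fault is confined to the top two points of one of four maternal outcomes, and no difference in language mix is shown. The other is that KC practice is wrongly coded for every Malay-form mother: this happens only if printed codes are entered and pooled without recoding, which no section states. What remains for that item is a mismatch in codes and wording that needs a rule before any use.

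**What to change.** 1. Check the Malay form as administered against Appendix E(b).
2. For any further use, give point 5 its own Malay label, and use the same KC-practice question and the same Yes/No codes in both forms.
3. Record form language for each mother and tabulate it by group. For returned questionnaires it can be read off the form if these were kept.
4. Recruitment is reported for 2018 to 2019, so for data already collected report stress again as a sensitivity analysis. Score points 4 and 5 as one value in both languages, before any reverse scoring. If the conclusion holds, the label fault does not drive it.
5. If the KC-practice item is used, recode it by form language and report the ever and in-NICU answers separately, not as one variable.

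The cost is one corrected label, one aligned item, one recorded variable and one extra run of an analysis already planned. No new data collection is needed.
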